### Progression-free Survival (PFS)

Progression-free survival is calculated as the time from randomization to the first documented progression or death due to any cause during or after the treatment period, whichever occurs first. The progression date will be assigned to the earliest time when any progression is observed without prior missing assessments. If withdrawal of consent or loss to follow-up occurs before documented progression or death, then these observations will be censored at the date when the last complete tumor assessments determined a lack of progression.

For subjects who do not develop progressive disease at the time of analysis, if the response from the last visit was 'not evaluable', the most prior visit date with complete evaluation indicating no progressive disease will be used as the censor date.

For subjects who received other anti-CLL or anti-neoplastic therapy before PD, the most prior visit date with complete evaluation indicating no progressive disease will be used as the censor date.

If a subject has 2 or more consecutive missing response assessments followed by PD, the prior assessment date with complete evaluation indicating no progressive disease will be used as the censor date.

If a subject died without PD while in study but there are 2 or more consecutive missing response assessments before death date, the prior assessment date with complete evaluation indicating no progressive disease will be used as the censor date.

Kaplan-Meier product limit methods will be used to estimate the survival functions for treatment arm. Median PFS along with two-sided 95% CIs will be estimated.

### **Event-free Survival (EFS)**

Event free survival (EFS) is the interval between the start of treatment to the first sign of disease progression, or treatment for relapse, or death (whichever occurs first).

The censoring rules are the same as PFS, except that start of a new anti-CLL or anti-neoplastic therapy is considered an event.

Kaplan-Meier product limit methods will be used to estimate the survival functions for each treatment arm. Median EFS along with two-sided 95% CIs will be estimated.

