10.4.1.7. Prohibited Concomitant Therapy

Concomitant use of other CLL therapy or investigational therapies while the subject is on study drug is prohibited.

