14. OTHER ASSESSMENTS

14.1. Assessments Following Treatment Discontinuation

Subjects will continue in the study and receive study drug until discontinuation from the study for any of the following reasons: disease progression; AEs that, in the judgment of the Investigator, may cause severe or permanent harm or which rule out continuation of study drug, subject withdraws consent, subject is lost to follow-up, death, protocol violation that may rule out continuation of study drug, other reasons that in the Investigators judgment that may rule out continuation of study drug.

For those subjects who discontinue study drug for reasons other than disease progression or withdrawal of consent, study visits should continue every 28 days to assess response until documentation of disease progression or until a new CLL therapeutic regimen is started, whichever comes first. During these visits only the following assessments will be required: hematology, ECOG performance status, evaluation of constitutional symptoms, physical exam for liver, spleen and lymph nodes, adverse events, second primary malignancies, concomitant medications/therapies, and assessment of response.

For subjects who develop PD characterized by transformation to a more aggressive histology [i.e. Richter's syndrome (lymphomas) or prolymphocytic leukemia], this diagnosis should be established by lymph node biopsy whenever possible.

Subjects who are discontinued from the study drug for any reason, except for withdrawal of consent, will be followed for survival, second primary malignancies and subsequent CLL therapies until the study is closed when 80% of the subjects randomized to the study have progressed or died or up to five years after the last subject was randomized, whichever occurs later.

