15.3. Efficacy Evaluation

Efficacy analysis will be performed on intent-to-treat population. Adjudicated response will be used for these analyses.

Response

Response, including evaluation of minimal residual disease (MRD), will be assessed by iwCLL guidelines for diagnosis and treatment of CLL (Hallek, 2008). The response rate based on the best response during the treatment period and the relative proportions in each response category will be examined. Exact test procedures for proportions will be used to compare response rate between the treatment arms. Distributions of the responses into the response categories (CR, CRi, nPR, PR, SD, PD) will be provided for each treatment arm. Response rates (CR+CRi+nPR+PR) together with confidence intervals will be provided for each regimen, both for the entire population and for the subgroups defined by the stratification factors.

Responses from subjects after they received other anti-cancer treatments will not be counted, however, these subjects will be included in the denominator.

Duration of Response

Duration of response is defined as the time from the first visit where PR, CRi, or CR was documented to PD. Duration of response will be censored at the last date that the subject was known to be progression-free for: 1) subjects who have not progressed at the time of analysis; 2) subjects who have withdrawn consent or are lost to follow-up prior to documentation of progression.

A two-sided log rank test stratified by the 3 strata used in the randomization at 0.05 significance level will be used to test the duration of response between the two treatment arms.

Time to Response

Time to response is calculated as the time from randomization to the first documented date of PR, CRi or CR based on iwCLL guidelines.

Progression-free Survival (PFS)

Progression-free survival is calculated as the time from randomization to the first documented progression or death due to any cause during or after the treatment period, whichever occurs first. The progression date will be assigned to the earliest time when any progression is observed without prior missing assessments. If withdrawal of consent or loss to follow-up occurs before documented progression or death, then these observations will be censored at the date when the last complete tumor assessments determined a lack of progression.

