### **Time-to-Progression (TTP)**

TTP is defined as the time from randomization to the first documented progression. For subjects who do not progress during the study, TTP will be censored at the last adequate response assessment showing evidence of no disease progression. TTP is the same as PFS when there is no death. The same censoring rules for PFS applies except that death is not counted as an event.

Kaplan-Meier product limit methods will be used to estimate the survival functions for each treatment arm. Median TTP along with two-sided 95% confidence intervals (CI) will be estimated.

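### The SAP counts any new anti-neoplastic therapy as an EFS event, although EFS is defined by treatment for relapse, so therapy for a second primary malignancy falls in

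*SAP*

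**What the plan says.** SAP section 11, under Event-free Survival, measures EFS from the start of treatment to the "first sign of disease progression, or treatment for relapse, or death (whichever occurs first"). Protocol 15.3 gives the same definition. The SAP's next sentence sets the working rule: "The censoring rules are the same as PFS, except that start of a new anti-CLL or anti-neoplastic therapy is considered an event". It gives no limit by indication, and neither document defines anti-neoplastic therapy.

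The PFS rule in SAP section 11 treats the same therapy differently. It begins "For subjects who received other anti-CLL or anti-neoplastic therapy before PD, the most prior visit date" and goes on to make the last complete evaluation without progression the censoring date. TTP follows by reference: "The same censoring rules for PFS applies except that death is not counted as an event". Protocol 15.3 has no censoring at new therapy for PFS, which runs to "first documented progression or death due to any cause during or after the treatment period, whichever occurs first".

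Protocol 14.1 keeps 28-day response visits going after study drug stops, for reasons other than progression or withdrawal of consent, "until documentation of disease progression or until a new CLL therapeutic regimen is started, whichever comes first". Second primary malignancies are an event of interest, reported through survival follow-up (protocol 8.1.7, SAP 5.1.3).

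**The concern.** The definition and the rule that implements it do not describe the same endpoint. The definition has one therapy component, treatment for relapse. The rule adds any anti-neoplastic therapy. A programmer would follow the rule. A reader of the report would go by the definition.

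The two part company for a subject who starts treatment for a second cancer while the CLL is controlled. Under the rule that subject has an EFS event on that day, without progression, relapse therapy or death. EFS would then partly measure the occurrence and treatment of other cancers, in a trial that follows those cancers as a safety question. For PFS and TTP the issue is a different one: CLL follow-up that is still being collected would not be used.

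**Working it through.** The plan states no figure on this point, so there is none to reproduce. The check compares the texts and then illustrates the size.

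**1. Definition against rule (SAP section 11, EFS).** Therapy for CLL relapse is an event under both. Therapy for another cancer is not an event under the definition but is one under the rule. Reading anti-neoplastic as a second name for CLL therapy makes the words redundant, because anti-CLL is already listed. Reading it as therapy for transformed disease adds little, because protocol 14.1 already treats transformation as progression.

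**2. Can the case arise?** Yes. Protocol 10.4.1.7 says: "Concomitant use of other CLL therapy or investigational therapies while the subject is on study drug is prohibited". It does not name treatment of another cancer. If study drug is stopped, protocol 14.1 still continues response visits, because therapy for another cancer is not a new CLL regimen.

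**3. PFS and TTP.** The subject is censored at the last complete evaluation before the therapy. A later progression or death is left out of PFS, and a later progression out of TTP, even when observed at a scheduled visit. The one general efficacy sensitivity analysis in SAP section 11 changes the assessor (investigator in place of adjudicated response), not the therapy rule.

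**4. Size, as an illustration only.** Inputs:
- Median PFS of 5.5 months, from the sponsor's earlier CLL-001 study (protocol 5.3.2.3).
- Median PFS of 19.4 months, from an earlier relapsed/refractory study that added rituximab at progression (protocol 5.3.2.1).
- Rate of starting therapy for a second primary: 1, 3 or 5 per 100 person-years. This is assumed; it is not in the documents.
- 35 subjects per arm, 105 in all (SAP 6.1). SAP section 3 reports 104 enrolled, which makes no practical difference.

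The two causes are treated as independent with constant hazards, and PFS stands in for EFS without the added component. With λ = ln 2 / (median PFS) and μ = rate / 12 per month:
- share of first EFS events due to second-primary therapy = μ / (λ + μ)
- median EFS under the SAP rule = ln 2 / (λ + μ)

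Example: median 19.4 months and 5 per 100 person-years give λ = 0.6931 / 19.4 = 0.03573 and μ = 0.05 / 12 = 0.00417. The share is 0.00417 / 0.03990 = 10.4%, and the median is 0.6931 / 0.03990 = 17.37 months.

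| Median PFS (months) | Assumed rate per 100 person-years | Share of first EFS events | Median EFS under the rule (months) | Expected per 35 | Expected per 105 |
|---|---|---|---|---|---|
| 5.5 | 1 | 0.7% | 5.46 | 0.2 | 0.7 |
| 5.5 | 3 | 1.9% | 5.39 | 0.7 | 2.0 |
| 5.5 | 5 | 3.2% | 5.32 | 1.1 | 3.4 |
| 19.4 | 1 | 2.3% | 18.96 | 0.8 | 2.4 |
| 19.4 | 3 | 6.5% | 18.13 | 2.3 | 6.9 |
| 19.4 | 5 | 10.4% | 17.37 | 3.7 | 11.0 |

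The expected counts suppose that every subject eventually has an event. The effect is small when disease control is short and grows with its length.

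**The case against.** **The term is undefined.** Neither rule mentions second primaries, and the text does not settle whether, say, local excision of a skin cancer is the start of a new therapy. This stands in part: that the rule reaches second-primary therapy is an inference. It is still the plain reading, and leaving the term undefined does not remove the conflict.

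**The breadth is not foreign to the plan.** Protocol 15.3 does not count responses after other anti-cancer treatments, whatever their indication, and allows an OS sensitivity analysis censored at such therapy. Some second-primary regimens may also act on CLL. This stands for PFS and TTP, where the choice of therapies that censor is a reasonable trade-off. It does not rescue EFS, because neither provision changes what an EFS event is.

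**Subjects may not stay on lenalidomide.** Protocol Table 5 and the note below it, with section 10.5, let the investigator interrupt or stop drug for adverse events, and nothing says that subjects treated for a second cancer generally continue. True, but the EFS rule applies whether or not drug continues.

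**Stronger readings that a reader might infer.** One is that treating a second cancer is scored as CLL failure. That does not fit PFS or TTP, where the subject is censored, and it is loose even for EFS, which counts death from any cause. Another is that the better-controlled arm is penalised. The documents do not show this. With an equal μ in each arm, ln 2 / (λ + μ) keeps the order of the arms. If the two anchors were two arms, the gap of 19.4 − 5.5 = 13.9 months would shrink to 17.37 − 5.32 = 12.05 months at 5 per 100 person-years, without reversing. A firm count of affected subjects is not supported either, since no rate is given.

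**Conclusion.** The EFS rule in SAP section 11 contradicts the definition beside it and in protocol 15.3. On its plain reading, therapy for a second primary malignancy without CLL relapse counts as an EFS event outside the endpoint's definition. This is more than missing detail, because the SAP states the conflicting rule.

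The true size is unknown. The range of about 0.7% to 10.4% of first EFS events rests wholly on the assumed therapy rates, constant and independent hazards, and two borrowed medians. EFS, PFS and TTP are secondary endpoints, estimated by Kaplan-Meier curves and medians per arm; the primary safety endpoint is unaffected. For PFS and TTP the documents support only a loss of collected follow-up, with bias if the censoring is informative, in a direction that cannot be told in advance.

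**What to change.** - **EFS rule (SAP section 11).** Replace the anti-CLL or anti-neoplastic wording with: new therapy given for CLL (including transformed CLL). Add that therapy for another cancer is not an event and that the subject stays at risk. Without that clause the sentence would still import the PFS censoring rule, and these subjects would be censored for EFS instead.
- **EFS sensitivity analysis.** Keep the present any-anti-neoplastic rule in this role, with the term defined.
- **PFS and TTP.** Leave the main rule. Add a sensitivity analysis that follows subjects through non-CLL therapy to progression, death (PFS only) or the last complete assessment.

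The cost is a few sentences, two sensitivity runs and an indication flag for each subsequent therapy. The 28-day follow-up visits already record concomitant therapies and second primaries (protocol 14.1). The drawback is that subjects given a second-primary regimen with some CLL activity stay at risk in the main EFS analysis; the sensitivity analysis shows how much that matters.

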### **Time-to-Progression (TTP)**

TTP is defined as the time from randomization to the first documented progression. For subjects who do not progress during the study, TTP will be censored at the last adequate response assessment showing evidence of no disease progression. TTP is the same as PFS when there is no death. The same censoring rules for PFS applies except that death is not counted as an event.

Kaplan-Meier product limit methods will be used to estimate the survival functions for each treatment arm. Median TTP along with two-sided 95% confidence intervals (CI) will be estimated.

### **Overall Survival (OS)**

Overall survival is calculated as the time from randomization to death from any cause. OS will be censored at the last date that the subject was known to be alive for subjects who were alive at the time of analysis and for subjects who have withdrawn consent or lost to follow-up before death was documented.

The analysis of OS will include survival information for all randomized subjects. Subjects who discontinued from the treatment phase of the study and who had possibly received other anti-cancer therapies and then subsequently died will be included in the analysis as death.

Kaplan-Meier product limit methods will be used to estimate the survival functions for each treatment arm and overall. Median OS along with two-sided 95% confidence intervals (CI) will be estimated.

## 12. SAFETY ANALYSIS

All safety analyses will be based on subjects who receive at least one dose of study drug and will be presented by treatment arm. Safety measurements will include adverse events, clinical laboratory information, vital signs, and deaths. All analyses of safety data will be conducted using the safety population unless specified otherwise.

### 12.1. Adverse Events

The adverse events of Neutropenia, Anemia and Thrombocytopenia will be analyzed according to the grading system as recommended by the IWCLL guidelines for the diagnosis and treatment of CLL (Hallek, 2008).

The adverse event of Tumor Lysis Syndrome (TLS) will be analyzed according to the grading system as recommended by Cairo-Bishop grading system.

Treatment emergent adverse events (AEs) will be summarized by treatment arm and overall. A treatment emergent adverse event is defined as any AE occurring or worsening on or after the first treatment of any study drug, and within 30 days after the last dose of the last study drug received. Adverse events will be presented in descending order of frequency (for all subjects) by SOC, and then within each SOC, by decreasing order of preferred term. Adverse events are documented on the CRF together with their severity, according to the NCI CTCAE version 3.0 or higher, also referred to as NCI toxicity grading. For the categorization of the adverse events, the MedDRA® dictionary (version 15.0) will be used.

AE frequency will be tabulated by body system, MedDRA preferred term for each treatment regimen during the Treatment Phase as well as for the Follow-up Phase when appropriate. In the by-subject analysis, a subject having the same event more than once will be counted only once and by the greatest severity. AEs will be summarized by worst NCI CTCAE version 3.0 grade. In the case that the AEs or event frequencies are judged to be clinically important, an exact test may be used to analyze the difference between the treatment arms. Events of interest will also be summarized by treatment cycles.

AEs leading to death or to discontinuation from treatment, events classified as NCI CTCAE version 3.0 Grade 3, 4, and 4 AEs, treatment-related events, serious adverse events (SAEs) and events of interest (including second primary malignancies) will be summarized separately.

Individual AE listings by subject will be provided.

As an exploratory analysis, AEs will be summarized by treatment arm and by subgroup (i.e., relapse vs. refractory, age <65 vs. age ≥65, lines of prior CLL treatment, gender).

Adverse events (AE) will be classified using the Medical Dictionary for Regulatory Activities (MedDRA) classification system. The severity of the toxicities will be graded according to the NCI CTCAE version 3.0 whenever possible.

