consent, will be followed every 12 weeks for survival, secondary primary malignancies and subsequent CLL therapies until the study is closed (see Figure 1 Overall Study Schema).

Study will be closed once 80% of the subjects randomized to the study have progressed or died or up to five years after the last subject was randomized, whichever occurs later. All subjects ongoing on study drug at the time the study is closed will be transferred to lenalidomide on a free basis in agreement with the site principal investigator and local regulations.

Response Assessment

Tumor response will be assessed according to the iwCLL guidelines for the diagnosis and treatment of CLL (Hallek, 2008), including CR, CRi, nPR, PR, SD and PD. Evaluation of response will be performed after 3 cycles of therapy and every 4 weeks thereafter.

For those subjects who reach PR, CRi or CR, a CT scan of the neck, chest, abdomen and pelvis to assess lymphadenopathies will be performed at the PR and CR/CRi confirmation visits (≥ 8 weeks to ≤ 12 weeks)after all clinical and laboratory response criteria have been met for PR or CR/CRi). Those subjects whose response was down-graded based on the CT scan interpretation at the PR or CR/CRi confirmation visit will have the CT scan repeated 4 months later at the location where remaining disease has been documented, as long as clinical and laboratory response remains present to try to document further improvement.

For those subjects who reach CR or CRi, a bone marrow aspirate and bone marrow biopsy will be performed at the CR/CRi confirmation visit (≥ 8 weeks to ≤ 12 weeks after all clinical and laboratory response criteria have been met). If the bone marrow is hypocellular, a repeat specimen should be obtained after 4 weeks, provided that the blood counts have recovered. If the bone marrow biopsy shows disease involvement (30% or greater lymphocytes, or nodules positive for B-CLL cells by immunohistochemistry), an additional bone marrow biopsy and aspirate will be taken 4 months later as long as clinical and laboratory response remain in CR or CRi response status to try to document further improvement.

MRD status will be evaluated for those subjects who reach CR or CRi. A peripheral blood and bone marrow aspirate sample will be collected for MRD analysis by flow cytometry at the CR/CRi confirmation visit.

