- t. AEs will be reported from the time informed consent is signed to 30 days post last dose of study drug. AEs that lead to study discontinuation should be followed until resolution or stabilization. For subjects who discontinue study treatment but continue to be followed every 28 days until PD or new CLL therapy, AEs will be reported until 30 days post last dose of study drug or until study discontinuation, whichever occurs last. SAEs will be reported from time informed consent form is signed to 30 days post last dose of study drug. SAEs will be reported at any time post last dose of study drug if it is considered related to study drug.
- u. Second primary malignancies will be monitored as events of interest and must be reported as serious adverse events regardless of the treatment arm the subject is in. This includes any second primary malignancy, regardless of causal relationship to study drug, occurring at any time for the duration of the study, from the time of signing the informed consent up to and including the survival follow up period. Subjects will be followed until 80% of the subjects have progressed or died or up to five years after the last subject was randomized, whichever occurs later. Events of second primary malignancy are to be reported using the SAE report form and must be considered an "Important Medical Event" even if no other serious criteria apply; these events must also be documented in the appropriate page(s) of the CRF and subject's source documents. Documentation on the diagnosis of the second primary malignancy must be provided at the time of reporting as a serious adverse event (e.g., any confirmatory histology or cytology results, X-rays, CT scans, etc.).
- v. Investigators to provide assessment of CR, CRi, nPR, PR, SD, and PD based on laboratory, physical exam, assessment of constitutional symptoms and if appropriate CT scan findings (CT scans are to be performed at baseline and to confirm PR or CR/CRi). For confirmed PR, nPR or CR/CRi, response must be maintained for ≥ 8 weeks as per the iwCLL guidelines for the diagnosis and treatment of CLL (Hallek, 2008) Tumor response will be assessed according to

- the iwCLL guidelines (Hallek, 2008) for the diagnosis and treatment of CLL (Hallek, 2008), including CR, CRi, nPR, PR, SD, and PD. Evaluation of response will be performed after 3 cycles of therapy and every 4 weeks thereafter.

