21. APPENDICES

21.1. Adverse Event

An adverse event (AE) is any noxious, unintended, or untoward medical occurrence occurring at any dose that may appear or worsen in a subject during the course of a study. It may be a new intercurrent illness, a worsening concomitant illness, an injury, or any concomitant impairment of the subject's health, including laboratory test values (as specified by the criteria below), regardless of etiology. Any medical condition that was present prior to the signing of informed consent and that remains unchanged or improved should not be recorded as an AE. If there is a worsening of that medical condition, this should be considered an AE. A diagnosis or syndrome should be recorded on the AE page of the Case Report Form rather than the individual signs or symptoms of the diagnosis or syndrome.

All AEs will be recorded by the Investigator(s) from the signing of informed consent to the treatment discontinuation visit. All AEs that lead to study discontinuation should be followed until resolution or stabilization. For subjects who discontinue study treatment but continue to be followed every 28 days until PD or new CLL therapy, AEs will be reported until 30 days post last dose of study drug or until study discontinuation, whichever occurs last. SAEs will be reported from time informed consent form is signed to 30 days post last dose of study drug. SAEs will be reported at any time post last dose of study drug if it is considered related to study drug. AEs will be recorded on the AE page of the eCRF and in the subject's source documents.

Abnormal laboratory values defined as adverse events

An abnormal laboratory value is considered to be an AE if the laboratory abnormality is characterized by any of the following:

- Results in discontinuation from the study.
- Requires treatment, modification/interruption of study drug dose, or any other therapeutic intervention.
- Is judged by the Investigator(s) to be of significant clinical importance.

If a laboratory abnormality is one component of a diagnosis or syndrome, then only the diagnosis or syndrome should be recorded on the AE page of the eCRF. If the abnormality was not a part of a diagnosis or syndrome, then the laboratory abnormality should be recorded as the AE.

Serious adverse event

A serious adverse event (SAE) is any AE which:

- Results in death

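### Follow-up Phase AE percentages by arm depend on how many subjects, and for how long, stay on 28-day visits, because ordinary AEs after day 30 are collected only from them

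*SAP*

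**What the plan says.** **Collection.** Protocol Table 2, footnote t, sets the base window: "AEs will be reported from the time informed consent is signed to 30 days post last dose of study drug". For subjects who have stopped treatment but remain on 28-day visits, the same footnote extends it: "AEs will be reported until 30 days post last dose of study drug or until study discontinuation, whichever occurs last".

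Table 2, footnote c, and section 14.1 say who has those visits: "For those subjects who discontinue study drug for reasons other than disease progression or withdrawal of consent, study visits should continue every 28 days". The visits run until progression or a new CLL regimen, and adverse events are among the required assessments.

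Other subjects, except those who withdraw consent, are "followed every 12 weeks for survival, secondary primary malignancies and subsequent CLL therapies until the study is closed" (Synopsis). In Table 2 the adverse-event row has no mark in the 12-week column, while the second-primary-malignancy row does. One exception applies to everyone: "SAEs will be reported at any time post last dose of study drug if it is considered related to study drug".

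Appendix 21.1 states a different base window: "All AEs will be recorded by the Investigator(s) from the signing of informed consent to the treatment discontinuation visit".

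**Analysis.** SAP 12: "All safety analyses will be based on subjects who receive at least one dose of study drug and will be presented by treatment arm". The section allows exceptions where they are specified. SAP 12.1 plans AE tables "for each treatment regimen during the Treatment Phase as well as for the Follow-up Phase when appropriate" and specifies no exception for them. It also permits an exact test between arms where events are judged clinically important. SAP 6.5.1 lets a percentage denominator be either the analysis population or the subjects with non-missing data, and does not say which applies here. The Follow-up Phase is not defined.

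**The concern.** The reason for stopping decides whether a subject's later AEs can be seen at all. A subject who stops for progression gives ordinary AEs to day 30 at most, which is also where the SAP's treatment-emergent window ends. A subject who stops for toxicity can go on giving AEs for months. If both sit in the denominator of a Follow-up Phase table, the percentage mixes the AE rate with the amount of observation.

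The arms differ in starting dose, so the mix of stop reasons may itself differ by arm. An arm with more toxicity stops would then gain observation time, and with it apparent late AEs, at an unchanged risk per month. Type and frequency of AEs are the primary endpoint, so a by-arm AE table of this kind is likely to be read as a comparison even if the SAP does not intend one.

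**Working it through.** The documents give no expected Follow-up Phase AE rate, so there is no planned figure to reproduce. The check traces who is observed and then illustrates the effect.

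**1. Who can contribute after day 30**

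| Reason for stopping | Ordinary AEs after day 30 | In the safety-population denominator |
|---|---|---|
| Adverse event, protocol violation, other | Yes, until progression or new CLL therapy | Yes |
| Progression | No | Yes |
| Consent withdrawal | No | Yes |
| Death, loss to follow-up | No usable follow-up time | Yes |

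Drug-related SAEs are reportable at any time. Second primary malignancies are also followed at the 12-week contacts.

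**2. Formula**

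Let s be the share of an arm on 28-day visits, λ the AE rate per month, and m the mean months of AE collection after day 30 (exponentially distributed). The chance of at least one AE for a followed subject is

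q = λ / (λ + 1/m).

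The expected percentage with the whole arm as denominator is s × q. If λ and m are the same in two arms, their ratio is s₁/s₂ whatever λ and m are.

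**3. Inputs**

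- Arm size 35 (SAP 6.1).
- Reference share: in CLL-001 (protocol 5.3.2.3), 29% stopped for AEs and 10% for other reasons, so s = 29% + 10% = 39%. This is pooled, and assumes that every such subject would have entered 28-day visits.
- Assumptions, not in the documents: s from 20% to 60%, λ from 0.1 to 0.5 per month, m from 2 to 8 months, with λ and m equal in all arms.

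**4. Results**

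At λ = 0.3 and m = 4, q = 0.3 / (0.3 + 0.25) = 54.5%.

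| Share followed | Whole-arm percentage | Subjects of 35 | Range over all λ and m |
|---|---|---|---|
| 20% | 10.9% | 3.8 | 3.3% to 16.0% |
| 39% | 21.3% | 7.4 | 6.5% to 31.2% |
| 60% | 32.7% | 11.5 | 10.0% to 48.0% |

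A milder contrast of 30% against 50% gives 16.4% (5.7 subjects) against 27.3% (9.5), a ratio of 0.50/0.30 = 1.67. The AE rate is the same in every row.

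Length of follow-up acts separately. With s = 39% and λ = 0.3 in both arms, m = 2 gives 14.6% and m = 8 gives 27.5%.

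**5. What removes the effect**

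Restricting the denominator to followed subjects removes s: each arm shows q, 54.5% in the main case. It does not remove m: at λ = 0.3, q is 37.5% for m = 2 and 70.6% for m = 8. Events per subject-month remove both, since expected events per followed subject are λ × m and (λ × m)/m = λ, here 0.3 per month in either arm. A subject count and a rate are therefore both needed.

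**The case against.** Several points on the other side stand.

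- **The table is conditional and secondary.** It is planned only where appropriate. The main AE summary covers first dose to 30 days after last dose and does not use this denominator. The exact test is optional and not aimed specifically at the Follow-up Phase.
- **The denominator is not fully fixed.** SAP 6.5.1 leaves a non-missing-data denominator open, which could remove the effect of the share followed. But nothing selects it for this table, and AE data normally hold no missing record for an unobserved subject. The default in SAP 12 therefore governs.
- **The size is not established.** A reader might infer a two- to threefold distortion. That only restates assumed shares: 40/20 = 2 and 60/20 = 3. The one documentary figure is a pooled 39%, and all arms escalate toward the same 25 mg maximum. The CLL-001 median PFS of 5.5 months cannot stand in for off-drug follow-up either, because it runs over the whole trial and 28-day visits also end at new CLL therapy. Likewise, a chance of about 60% of nominal p < 0.05 at 35 per arm arises only with 20% against 60% followed, λ = 0.3, m = 4, a normal approximation and any AE as the outcome. The SAP tabulates by preferred term, where counts are smaller.
- **Stopping other than for progression is not the same as stopping for toxicity.** A reader might infer that toxicity is systematically counted twice. The documents do not support that in general: some stops are for other reasons, and deaths and losses add no follow-up. The driver is time on 28-day visits.

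Nor does the SAP say that unobserved subjects are to be regarded as event-free. That is the arithmetic effect of the default denominator, not a stated rule.

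**Conclusion.** The point holds as a defect of one planned table. Under the protocol's collection rules and the SAP's default population, Follow-up Phase percentages for ordinary AEs depend on each arm's share and time on 28-day visits as well as on AE risk. At equal rates and equal follow-up length the ratio between arms equals the ratio of the shares followed. How far those shares differ in this trial cannot be told from the documents, so the figures above show direction and mechanism only.

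The documents do not support the stronger reading that the primary safety comparison is biased by this. The treatment-emergent tables stop at day 30, before collection becomes selective under footnote t. One reservation remains: Appendix 21.1 ends base AE recording at the treatment discontinuation visit, with an extension for subjects on 28-day visits. If sites followed that wording, the last part of the treatment-emergent window was not observed alike in all subjects. The selective collection after day 30 exists under either wording.

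**What to change.** In SAP 12.1:

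- Define the Follow-up Phase for ordinary AEs as day 31 after last dose to the end of 28-day visits.
- Use as denominator the subjects under 28-day AE collection, and report events per subject-month under collection.
- Show for each arm the number and share of treated subjects under observation, with total subject-months.
- Tabulate second primary malignancies and drug-related SAEs separately on all treated subjects, since these are sought beyond the 28-day visits.
- State that the exact between-arm test is not applied to the Follow-up Phase table and is limited to the treatment-emergent window.

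Reconcile Appendix 21.1 with Table 2, footnote t, so that this window is common to all treated subjects. Enrolment is complete (SAP 3), so the SAP should also state which window the database actually holds.

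The cost is SAP wording and a changed denominator in one set of tables. No new data are needed. The follow-up table becomes small and purely descriptive.
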